9.5.1. Study Drug Exposure

Study drug exposure (number of injections and total volume administered) will be summarized by treatment group for Day 0, Day 14, Day 28, and Day 42 using descriptive statistics for continuous variables.

9.5.2. Injection Site Adverse Events

The number and percentage of subjects with an injection site AE, by type (injection site reaction, ulceration, allergic reaction/hypersensitivity) and overall, will be summarized by treatment group at each weekly 'wound assessment and dressing change' visit and for the preand post-injection assessments on scheduled injection visit days (i.e., Days 0, 14, 28, and 42). The denominator for these percentages will be based on the number in the risk set following a given injection, which is the number of subjects who received that specific injection. The number and percentage of subjects for each grade within a given type of injection site AE will be summarized by treatment group at each assessment time point.

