Subjects in the *Placebo Group* will receive 16 injections of 0.5 mL VM202 vehicle in the ipsilateral calf of the affected foot with the target ulcer at each injection visit:

- Day 0 16 injections of 0.5 mL of VM202 vehicle
- Day 14 16 injections of 0.5 mL of VM202 vehicle
- Day 28 16 injections of 0.5 mL of VM202 vehicle
- Day 42 –16 injections of 0.5 mL of VM202 vehicle

Note: Visually, VM202 vehicle is indistinguishable from reconstituted VM202. The subject and clinician will not be able to distinguish placebo from VM202 injections.

Second, Third and Fourth Treatments. Prior to the study injections on Day 14, 28 and 42, vital signs, and concomitant medications will be documented. The target ulcer will be documented by photograph, surface area measurement, depth and volume. In addition, blood will be drawn for determination of copies of VM202, serum HGF (Day 28 only), and serum chemistry and hematology (Day 42 only). The occurrence of injection site reactions and AEs will be assessed prior to the study injections.

Post Injections. 1 to 3 hours post injection on Days 0, 14, 28 and 42, vital signs, and blood draw for determination of copies of VM202 will be performed, and the occurrence of injection site reactions and AEs will be assessed.

Subjects will continue to come to the clinic once a week for dressing changes and wound assessment until the ulcer has healed or study exit, whichever comes first. At these visits, vital signs, concomitant medications, target ulcer documentation

(photograph, surface area, depth, perimeter and volume measurements), and the occurrence of injection site reactions (if the visit occurs within 60 days) and AEs will be assessed.

All subjects will be assessed at Day 60, Day 74, Day 90, Day 120 and Day 210; at all these visits, vital signs, concomitant medications, assessment of AEs and, if applicable, target ulcer documentation (photograph, surface area, depth, perimeter and volume measurements) will be conducted.

The occurrence of injection site reactions will be assessed on Day 60.

Blood will be drawn for determination of serum HGF, and copies of VM202 on Days 60 and 90. Blood will be drawn for determination of serum chemistry and hematology on Days 90, 120 and 210. Blood will be drawn for determination HbA1c on Days 120 and 210.

ABI, TBI, and CWIQ will be determined on Day 120, and 210. TcPO₂ will be assessed as a sub-study at 3 -10 sites at these visits.

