3.4.13. DAY 60 ± 3 DAYS

The following procedures will be performed:

- Vital signs
- Concomitant medications
- Documentation of the target ulcer (photograph and measurements of surface area, depth, perimeter and volume) before and after debridement.
- Copies of VM202 in whole blood
- Serum HGF
- Injection site assessment
- Adverse event assessment

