4.2.11. INJECTION SITE REACTION ASSESSMENT

Local injection sites reactions will be assessed on Day 0 post injection, Day 14 pre and post injection, Day 28 pre and post injection, Day 42 pre and post injection, Day 60, and at each wound assessment/dressing change visit after the first injection visit and prior to Day 60. Injection site reactions will be reported on the Injection Site Adverse Event form. The location (calf area) and temporal relationship to the most recent study injections will determine whether the event is an injection site reaction or adverse event.

Table 6. Injection Reaction Assessment

ADVERSE EVENT	GRADE 1	GRADE 2	GRADE 3	GRADE 4	GRADE 5
Injection site reaction	Pain, itching, erythema	Pain or swelling, with inflammation or phlebitis	Ulceration or necrosis that is severe; operative intervention indicated		
Ulceration		Superficial ulceration < 2 cm size; local wound care; medical intervention indicated	Ulceration ≥2 cm size; operative debridement, primary closure or other invasive intervention indicated (e.g., hyperbaric oxygen)	Life-threatening consequences; major invasive intervention indicated (e.g., complete resection, tissue reconstruction, flap, or grafting	Death

Adverse Event	GRADE 1	GRADE 2	GRADE 3	GRADE 4	GRADE 5
Allergic reaction / hypersensitivity	Transient flushing or rash; drug fever < 38°C (<100.4°F)	Rash; flushing; urticaria; dyspnea; drug fever ≥38°C (≥100.4°F)	Symptomatic bronchospasm, with or without urticaria; parenteral medications(s) indicated; allergy-related edema/ angioedema; hypotension	Anaphylaxis	Death

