3. STUDY DESIGN

This is a phase III, randomized, double-blind, placebo-controlled, multicenter, 7-month study designed to assess the safety and efficacy of intramuscular injections of VM202 in the calf of diabetic patients with chronic nonhealing foot ulcers and concomitant PAD. Subjects with confirmed PAD and diabetes aged \geq 18 years to \leq 80 years diagnosed with nonhealing foot ulcers will be screened for study eligibility after giving informed consent.

At Screening, standard of care will be initiated that will continue for the duration of the study, as follows:

- Surgical debridement of necrotic tissue or devitalized tissue
- Use of appropriate off-loading when ambulating
- Maintenance of moist wound environment

Three hundred patients (from up to 30 study centers) who meet the eligibility criteria will be randomized in a 2:1 ratio to one of two treatment groups: 200 patients with VM202 (16 mg) plus standard of care or 100 subjects with placebo plus standard of care, respectively. Safety will be monitored throughout the study by an independent Data Safety Monitoring Board (DSMB, Section 8.5).

Patients will receive intramuscular injections in the ipsilateral calf of the affected foot with the target ulcer of either VM202 or placebo on Day 0, Day 14, Day 28, and Day 42 as follows:

Treatment: Days 0, 14, 28, and 42

TREATMENT]	DOSE VM20	FINAL DOSE		
GROUP	DAY 0	DAY 14	DAY 28	DAY 42	VM202 (mg)
VM202	4	4	4	4	16
Placebo	0	0	0	0	0

0 indicates injections of Placebo

VM202 will be delivered in a solution of 0.5 mg VM202 / mL. All subjects will receive sixteen (16) 0.5-mL intramuscular injections of VM202 or placebo at each injection visit.

The schedule of study visits and the clinical parameters that will be measured at the visits are summarized in Table 1 to Table 3 below.

The subjects' target ulcer will be evaluated by photograph, surface area, depth, perimeter and volume measurements. Subjects must have a non-healing ulcer on Day 0 that meets study entry inclusion criterion # 5 and does not meet exclusion criterion #6 to be eligible for study participation. Subjects will continue to come to the clinic once a week for dressing changes and wound assessment until the ulcer has healed or study exit, whichever comes first. Measurement of the target ulcer will be performed at each follow-up visit until complete wound closure or study exit.

Further details on the study procedures and conduct are provided in the protocol.

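### The injection-site AE incidence summary in SAP 9.5.2 does not name the Day 60 assessment, the only fixed check after the day of the last injection

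*SAP*

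**What the plan says.** **Protocol.** Section 4.2.11 sets the schedule: Day 0 post injection, Days 14 and 28 pre and post, then "Day 42 pre and post injection, Day 60, and at each wound assessment/dressing change visit after the first injection visit and prior to Day 60". Section 3.2 repeats it: "The occurrence of injection site reactions will be assessed on Day 60". The procedure list under "3.4.13. DAY 60 ± 3 DAYS" includes an injection site assessment. Two further visits carry the check if they fall before Day 60: the healing-confirmation visit (3.4.18) and the early-withdrawal visit (3.5.2).

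**SAP schedule.** Table 2 marks an injection site reaction assessment at Day 60. SAP section 3 says that subjects attend "once a week for dressing changes and wound assessment until the ulcer has healed or study exit", whichever comes first.

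**SAP analysis.** In 9.5.2 the number and percentage of subjects with an event, by type and overall, "will be summarized by treatment group at each weekly 'wound assessment and dressing change' visit" and at the pre- and post-injection "assessments on scheduled injection visit days (i.e., Days 0, 14, 28, and 42"). The denominator is "the number in the risk set following a given injection, which is the number of subjects who received that specific injection". A last sentence covers severity: the numbers by grade within type "will be summarized by treatment group at each assessment time point".

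**The concern.** The incidence sentence gives a closed list of visits, and Day 60 is not on it. By contrast, SAP 9.5.4 (vital signs) covers every visit and 9.5.5 (laboratory values) every scheduled follow-up visit. A programmer following 9.5.2 literally would leave out a safety assessment that the protocol requires.

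The omission falls at an awkward point. Between Day 42 and Day 60 the only checks named for the table are the weekly ones, and these depend on the ulcer still being open. The number of tabulated checks after the fourth injection therefore depends on the efficacy outcome. The denominator does not adjust for this: a subject who received the injection but had no later tabulated check counts as event-free. At stake is a descriptive safety table that could understate delayed local reactions, possibly unequally between arms.

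**Working it through.** There is no stated figure to reproduce. The check compares the schedule with the summary and counts visits.

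**1. Fixed assessments (Protocol 4.2.11) against those named in SAP 9.5.2**

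| Assessment | Protocol | Named in 9.5.2 incidence summary |
|---|---|---|
| Day 0 post | yes | yes |
| Day 14 pre, post | yes | yes |
| Day 28 pre, post | yes | yes |
| Day 42 pre, post | yes | yes |
| Day 60 | yes | no |

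Protocol: 1 + 2 + 2 + 2 + 1 = 8. Named in the SAP: 7. The missing one is Day 60.

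**2. Interval left to the weekly visits**

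- Nominal: 60 − 42 = 18 days.
- With the ±3-day windows: shortest (60 − 3) − (42 + 3) = 12 days; longest (60 + 3) − (42 − 3) = 24 days.
- Weekly visits in the nominal interval: about Days 49 and 56, for unhealed subjects only.

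**3. Checks after the day of the fourth injection, by healing status**

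- *Unhealed through Day 60:* about two weekly checks, both in the table. Day 60 is not named.
- *Healed between Days 42 and 60:* weekly checks up to healing are in the table. A confirmation check before Day 60 is possible but not named.
- *Healed by Day 42, not yet confirmed:* no weekly checks. The confirmation check, if before Day 60, and Day 60 itself are not named.
- *Healed and confirmed by Day 42:* only Day 60 remains, and it is not named. Confirmation comes 14 ± 5 days after healing, so this means healing by about Day 28 (42 − 14), or between Day 23 (42 − 19) and Day 33 (42 − 9) across the window.

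Confirmation may take place at an unscheduled visit (Protocol 3.4.18), and SAP 9.5 sends unscheduled-visit safety data to listings only.

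**4. Illustration of size (assumed inputs)**

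The documents give neither a healing rate at Day 42 nor a rate of delayed reactions. Let *h* be the proportion healed by Day 42 and *r* the true rate of reactions detectable at the later weekly checks. Assume *r* is the same in healed and unhealed subjects, and that the fourth injection is given regardless of healing. Then the tabulated rate = *r* × (1 − *h*). With *r* = 10%:

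| *h* | Subjects with no weekly check after Day 42, of 300 planned | Of 44 enrolled | Tabulated rate |
|---|---|---|---|
| 5% | 15 | about 2 | 9.5% |
| 10% | 30 | about 4 | 9.0% |
| 20% | 60 | about 9 | 8.0% |
| 30% | 90 | about 13 | 7.0% |

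The 44 is 7 + 5 + 16 + 16, from SAP section 1. If *h* were 5% on placebo and 30% on VM202, the two ends of the assumed range, equal true rates of 10% would be tabulated as 9.5% and 7.0%, a spurious gap of 2.5 percentage points. If *h* were equal in the two arms, both rates would be diluted and no gap would arise.

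**The case against.** **The grade summary may already include Day 60.** Its last sentence covers every assessment time point, SAP Table 2 marks Day 60 as one, and SAP 9.5 bases summaries on available data at scheduled visits. This is a fair reading and it stands as a qualification. It does not settle the matter: on that reading the incidence and grade summaries in one section cover different visits.

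**Day 60 may double as a weekly visit.** Protocol 3.4.9 folds the weekly wound evaluation into a study visit falling in the same week, so some unhealed subjects' Day 60 data could be tabulated as a weekly visit. But SAP 8.2 analyzes scheduled follow-up by the nominal visit on the record, and healed subjects have no weekly visit to fold in.

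**The general AE tables may capture the event.** SAP 9.5.3 plans treatment-emergent events by injection number, with no later injection to close the window for the fourth. However, Protocol 4.2.11 puts injection-site reactions on a separate form, SAP 4.3 lists them as a separate safety outcome, and the SAP does not say that this form feeds the 9.5.3 tables.

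**Stronger readings that the documents do not support.**
- A reader might infer that nothing fixed follows the last injection except Day 60. The Day 42 post-injection check, 1 to 3 hours after the fourth dose, is fixed and is tabulated. It cannot show delayed reactions, which is why the point is confined to the period after that day.
- A reader might infer that healed subjects lose all follow-up. They do not: the Day 60 check is still done, AEs are assessed through Day 210, and SAP 9.1 puts all collected data in listings. What is missing is a tabulation.
- A reader might infer that VM202 will look safer. That needs a healing difference by about Day 42 and delayed reactions in healed subjects. The sample-size assumptions (50% to 60% against 20% to 30%) concern closure by 4 months and do not establish an earlier difference.

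**Conclusion.** The point holds as a minor reporting gap in a descriptive safety analysis. The incidence summary in SAP 9.5.2 names seven of the eight fixed injection-site assessments; the missing one is the only fixed assessment after the day of the last injection. Subjects healed by about Day 42 have no later check named for the incidence table but remain in its denominator.

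The direction of any error in the overall rate is toward undercounting delayed reactions to the fourth injection. Its size is unknown: the figures above rest on assumed healing and reaction rates. A bias between arms is possible, not shown. No formal testing is planned for safety (SAP 9.5), and the primary analysis is unaffected.

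The early stop (SAP 10) limits the number of subjects affected but makes each event weigh more. If the 44 enrolled split about 2:1 into 29 and 15 and all received the fourth injection, one missed event is 1/29 = 3.4 percentage points on VM202 or 1/15 = 6.7 on placebo.

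**What to change.** In SAP 9.5.2:

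1. Add the Day 60, healing-confirmation and early-withdrawal assessments to the incidence summary, and state that the grade summary covers the same time points. Say explicitly that confirmation checks made at unscheduled visits are included, since SAP 9.5 would otherwise confine them to listings.
2. Add a per-subject row for any injection-site adverse event after injection *k*, pooling all assessments up to the next injection, or through Day 60 for the fourth. Keep the number who received that injection as its denominator. State whether data from the injection-site form also enter the 9.5.3 tables, so that the two can be read together.

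The cost is a few table rows and two or three sentences. The protocol already requires the data, so nothing new is collected. If the SAP is already final, its section 1 provides for deviations to be documented in the clinical study report, and the added rows can be reported that way.

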3.4.8.3. Post-Injection (2 Hours \pm 1 Hour post injection)

The following procedures will be performed 1-3 hours post injection:

- Vital signs
- Copies of VM202 in whole blood
- Injection site assessment
- Adverse event assessment

3.4.9. WOUND ASSESSMENT AND DRESSING CHANGES AFTER DAY 0

Following Day 0, subjects will come in once a week for dressing change and wound evaluation. If a study visit is already scheduled for that week, the dressing change and wound evaluation will occur as part of the study visit.

At these visits, the following assessments will be performed:

- Documentation of target ulcer (photograph and measurements of surface area, depth, perimeter and volume) before and after debridement.
- Vital signs (except for weight)
- Concomitant medications
- Injection site assessment (visits prior to Day 60)
- Adverse event assessment

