3.6.4. Dose and Administration

VM202 is supplied in a sterile glass vial containing study product. Before administration, it will be reconstituted with study pharmacist for a final VM202 concentration of 0.5 mg / mL. Each reconstituted vial is only to be used for one subject. The VM202 arm will receive only VM202 injections. The placebo group will receive only VM202 vehicle injections. All subjects will receive 16 injections in ipsilateral calf of the affected foot with the target ulcer at each injection visit (Days 0, 14, 28 and 42). A complete description of test article administration can be found in Appendix 7.

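### SAP 9.5.2 divides weekly-visit injection-site AE percentages by everyone injected, so subjects not examined at that visit count as reaction-free (minor)

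*SAP*

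**What the plan says.** SAP 9.5.2 plans injection-site AE counts and percentages "summarized by treatment group at each weekly 'wound assessment and dressing change' visit", and also at the pre- and post-injection assessments on Days 0, 14, 28 and 42. It calls the denominator a risk set following a given injection, "which is the number of subjects who received that specific injection". The Day 60 and healing-confirmation checks are not named among the tabulated assessments.

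Four other places bear on this:

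- **When the site is checked.** Protocol 4.2.11 requires the check before and after each injection (after only on Day 0), on Day 60, and "at each wound assessment/dressing change visit after the first injection visit and prior to Day 60".
- **When weekly visits end.** Under SAP 3, subjects attend "once a week for dressing changes and wound assessment until the ulcer has healed or study exit, whichever comes first". Protocol 3.2 has the same limit: "wound assessment until the ulcer has healed or study exit, whichever comes first".
- **Whether injections end at healing.** Protocol 3.6.4 says "All subjects will receive 16 injections in ipsilateral calf of the affected foot with the target ulcer at each injection visit". I found no rule in either document that ends injections when the ulcer closes.
- **General safety rule.** SAP 9.5 bases safety summaries on the data available at scheduled visits, sends unscheduled-visit data to listings only, and rules out imputation of missing values.

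**The concern.** The number injected is a sound denominator for the question of how many subjects reacted at any time after an injection. It does not suit a percentage tied to one visit, because a subject who was not there cannot contribute an event. Keeping that subject in the denominator amounts to imputing no reaction, which sits badly with SAP 9.5.

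Absence from weekly visits is not random. One of its causes is ulcer closure, which is the efficacy outcome. If VM202 closes more ulcers, more of its subjects are missing from the weekly rows, and its weekly reaction percentages are diluted more than placebo's. Subjects who withdraw or miss a visit are treated in the same way, and for them the problem can also reach the pre-injection rows. What is at stake is how local tolerability reads in a table that has no formal test beside it.

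**Working it through.** **Plan's own figure.** The documents give no injection-site AE rate to reproduce. The only figures used are the 4-month closure rates in SAP 6 (50-60% VM202, 20-30% placebo). To confirm that they are read correctly, I recomputed the stated power of 0.898 for 0.50 v 0.30 with 200 and 100 subjects:

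- pooled proportion = (200 × 0.50 + 100 × 0.30)/300 = 0.4333
- null SE = √(0.4333 × 0.5667 × 0.015) = 0.0607; alternative SE = √(0.25/200 + 0.21/100) = 0.0579
- continuity correction = 0.5 × 0.015 = 0.0075
- z = (0.20 − 0.0075 − 1.96 × 0.0607)/0.0579 = 1.27, giving power 0.898

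This matches. (Exact enumeration of Fisher's test gives 0.918; nothing below depends on the difference.)

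**Which rows are affected.** Protocol 3.4.9 folds a weekly visit into a study visit when both fall in one week: "If a study visit is already scheduled for that week, the dressing change and wound evaluation will occur as part of the study visit". From the schedule I infer stand-alone weekly visits at about Days 7, 21, 35, 49 and 56. A site might merge Day 56 into the Day 60 visit; Day 49 would then be the last such row. Healed subjects still attend injection days, so healing does not affect those rows.

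**Formula.** With all injected subjects as denominator:

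reported % = true % × (1 − u),

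where u is the share injected but not examined. The relative understatement is therefore u, whatever the true rate. This takes reactions to be independent of healing.

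**Assumed healing curves.** The documents do not give closure by week. I take a subject as unexamined if healed by the previous week, d = visit day − 7, with p the 4-month closure rate:

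- constant hazard: u = 1 − (1 − p)^(d/120)
- back-loaded (rising hazard): u = 1 − (1 − p)^((d/120)²)

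**Worked case, Day 56 (d = 49), closure 60% v 20%, constant hazard.** VM202: u = 1 − 0.40^(49/120) = 0.312. Placebo: u = 1 − 0.80^(49/120) = 0.087. An illustrative true rate of 10% in both arms is reported as 6.88% v 9.13%, a ratio of 0.75 instead of 1. At closure 50% v 30% it is 7.53% v 8.64%, a ratio of 0.87.

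**Relative understatement u, VM202 v placebo, over the SAP closure ranges:**

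| Visit | Constant hazard | Back-loaded |
|---|---|---|
| Day 7 | 0 v 0 | 0 v 0 |
| Day 21 | 7.8-10.1% v 2.6-4.1% | 0.9-1.2% v 0.3-0.5% |
| Day 35 | 14.9-19.2% v 5.1-8.0% | 3.7-4.9% v 1.2-1.9% |
| Day 49 | 21.5-27.4% v 7.5-11.7% | 8.1-10.6% v 2.7-4.3% |
| Day 56 | 24.7-31.2% v 8.7-13.6% | 10.9-14.2% v 3.7-5.8% |

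With back-loaded healing the Day 56 ratio is 0.89-0.95.

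**Equal healing.** With 30% closure in both arms and constant hazard, u is 13.6% in each at Day 56. A true 10% is reported as 8.64% in both arms: the ratio is right and the level is too low.

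**Scale at actual enrolment.** SAP 1 gives 7 + 5 + 16 + 16 = 44 subjects, about 29:15 at 2:1 (the actual split is not stated). One subject is then 1/29 = 3.4 points on VM202 and 1/15 = 6.7 points on placebo. The Day 56 gaps in the constant-hazard cases above are 9.13 − 6.88 = 2.25 points and 8.64 − 7.53 = 1.11 points.

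**The case against.** The strongest reply has five parts.

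1. **Healed subjects are still checked.** They are examined at every remaining injection visit, at Day 60, and at the confirmation visit if it falls before Day 60. A lasting reaction would show at the next pre-injection check, which is tabulated. This stands, and it confines the problem to particular rows. After the fourth injection it helps less, because no injection visit follows and SAP 9.5.2 does not name the Day 60 and confirmation checks.

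2. **Materiality is low.** Safety is descriptive, and at 44 subjects the illustrated distortion is less than one subject in either arm. This also stands and is why the point is minor.

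3. **Protocol 3.4.9 sets weekly visits after Day 0 without an until-healed limit.** If sites followed that text, the healing effect would vanish, though not the effect of withdrawals and missed visits. Protocol 3.2 and SAP 3 both state the limit, so the passages need reconciling.

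4. **The number injected is a legitimate denominator.** It is, for cumulative incidence per injection, and the fix keeps it for that use.

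5. **Dividing by the number examined selects subjects whose ulcers are still open**, a group formed after randomisation and possibly by treatment. This is a real cost and limits what the weekly rows can show.

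A reader might infer more: that the whole injection-site table flatters VM202 on tolerability, or that a third or more of VM202 subjects would be unexamined. The documents do not support either. Healing leaves the injection-day rows and Day 7 alone, the between-arm distortion needs VM202 to heal more, and the largest VM202 share under the SAP's closure rates and these healing curves is 31%.

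**Conclusion.** The concern holds for the weekly rows. As written, SAP 9.5.2 understates visit-specific injection-site AE percentages by the share of injected subjects not examined at that visit. For healing this means roughly Days 21, 35, 49 and 56. Under constant-hazard healing the understatement grows from about 8-10% v 3-4% (VM202 v placebo) at Day 21 to 25-31% v 9-14% at Day 56; with back-loaded healing it is 11-14% v 4-6% at Day 56. The imbalance between arms appears only if VM202 closes more ulcers.

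The size rests on three assumptions: the SAP's planning closure rates, a healing curve that the documents do not give, and reactions independent of healing. The 10% reaction rate is illustrative and does not affect the relative figures. Severity: minor.

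**What to change.** In SAP 9.5.2:

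- For each visit-specific percentage, use as denominator the safety-population subjects with an injection-site assessment recorded at that assessment, and show the number injected in a column beside it.
- Keep the number injected as denominator only for a cumulative incidence per injection, counting any reaction at any assessment up to the next injection (after the fourth, through Day 60). Name the Day 60 and healing-confirmation checks as included. Because SAP 9.5 sends unscheduled-visit data to listings only, state the exception for confirmation visits.
- Rest the between-arm comparison on the per-injection incidence.

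Also reconcile Protocol 3.4.9 with Protocol 3.2 and SAP 3 on when weekly visits end.

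The cost is a few sentences, one column and one short table. The data are already collected and trial conduct does not change. The drawbacks are that denominators vary by visit and that the weekly rows then describe only subjects still attending, mainly those with open ulcers. If the SAP can no longer be revised, the change can be reported as a documented deviation, which SAP 1 allows for.
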